3.3.5 Clinical coordinator / study nurse

Depending on the organization of the investigational site, a clinical coordinator / study nurse may be required to assist the principal investigator / treating neurologist in all aspects of subject's management. She/he will be responsible for scheduling visits and assessments as planned in the study protocol, recording concomitant medications, maintaining source documentation, and transcription of data into the eCRF. She/he will instruct the subjects on study drug administration, and collect, process, and send all blood and urine samples to the central laboratory. Additionally, she/he may be responsible for coordinating the conduct of:

- MRI
- PFTs

5 December 2018, page 75/376

- Ophthalmological and cardiac examination (except cardiac assessment on Day 1 and on day of re-initiation of study drug when post-dose monitoring is required [see Section 3.3.4]
- MS Functional Composite (MSFC) score •
- Symbol Digit Modalities Test (SDMT) •
- Patient-Reported Outcome (PRO) instruments •
- Fatigue Symptom and Impact Questionnaire-RMS (FSIO-RMS)
- 36-Item Short Form Health Survey version 2 (SF-36v2TM) •
- MS Patient Preference Questionnaire (if applicable) •
- Patient's Global Impression of Severity (PGI-S) of Fatigue •
- Work Productivity and Activity Impairment: MS (WPAI:MS). •

In the absence of a clinical coordinator / study nurse, the above tasks will be performed by the principal investigator or a co-investigator.

3.3.6 MRI staff

The MRI staff will be responsible for performing the MRI investigations according to the study MRI manual (separate document). Original data will be exported to the Medical Image Analysis Center (MIAC), c/o University Hospital Basel, Switzerland, and primary data will be stored at the study site.

3.3.7 Local neuroradiologist/radiologist

The local neuroradiologist will review the MRI images for safety purposes and will inform the principal investigator / treating neurologist of any findings of concern for the subjects' safety, including non-MS related findings detected on the MRI scan. She/he will not communicate any efficacy-related MRI results (e.g., lesion counts) to study staff or to the subject, unless deemed necessary for maintaining safety of the subject. Significant findings, which, in view of the local neuroradiologist, meet the definition of an AE must be assessed for seriousness, reported to the principal investigator / treating neurologist and recorded on the AE page of the eCRF. In the event of safety findings of potential clinical concern observed on the MRI scans at any visit during the study, the local neuroradiologist will conduct further examination, as per local standard practice, to rule out or confirm the diagnosis. She/he may support the principal investigator in making a decision on eligibility of the subject prior to randomization by reviewing historical MRI used to assess the eligibility of the subject in the study (i.e., active disease evidenced by one or more Gd+ lesion[s] of the brain on an MRI performed within 6 months prior to randomization).

The local radiologist will review the chest X-ray (CXR) images. At Visit 1 (Screening), the local radiologist will assess CXRs in order to exclude any subject with findings suggestive of active or latent tuberculosis (TB); any CXR that had been performed within 90 days prior to screening can be used; if available, there is no need to repeat CXR at

Screening). At EOT, the local radiologist will assess CXRs in order to characterize any pulmonary structural changes that could have occurred during treatment. She/he will inform the principal investigator / treating neurologist of any findings of concern for the subjects' safety. Significant findings, which, in view of the local radiologist, meet the definition of an AE, must be reported to the principal investigator / treating neurologist and recorded on the AE page of the eCRF.

Depending on site setting, the same local radiologist may review MRI images and CXR images or a local radiologist may review MRI images and another local radiologist may review CXR images.

3.3.8 Ophthalmologist

The ophthalmologist will review and interpret the ophthalmological examinations and optical coherence tomography (OCT) assessments as scheduled in the study protocol [see Section 7.3.9 and 7.3.10]. In the event of suspected clinically significant findings (e.g., macular edema), an unscheduled OCT examination should be performed by the ophthalmologist, and the principal investigator / treating neurologist will be notified for reporting of an AE. In the event of findings observed at any visit during the study, the ophthalmologist will conduct further examination, as per local standard practice, to rule out or confirm the diagnosis.

3.3.9 Pulmonary function laboratory technician or expert

The PFTs must be performed by experienced staff, such as a pulmonary function technician or expert, according to the American Thoracic Society (ATS) / European Respiratory Society (ERS) guidelines [Miller 2005a].

3.3.10 Pulmonologist

At sites participating in the DL_{CO} sub-study, a pulmonologist or a physician adequately trained in respiratory medicine will review DL_{CO} results. If clinically significant alterations in DL_{CO} variables indicating a pulmonary condition that could result in increased risk for the subject are observed, she/he may be prematurely discontinued from the study drug at the discretion of the principal investigator / treating neurologist. Significant findings, which in view of the pulmonologist meet the definition of an AE, must be reported to the principal investigator / treating neurologist and recorded on the AE page of the eCRF. In the event of findings observed at any visit during the study, the pulmonologist will conduct further examination, as per local standard practice, to rule out or confirm the diagnosis.

3.3.11 Dermatologist

A dermatologist will perform complete skin examination as scheduled in the study protocol [see Section 7.3.13].

Significant findings, which in view of the dermatologist meet the definition of an AE, must be reported to the principal investigator / treating neurologist and recorded on the AE page of the eCRF. In the event of findings observed at any visit during the study, the dermatologist will conduct further examination, as per local standard practice, to rule out or confirm the diagnosis.

3.4 Study committees

3.4.1 Independent Data Monitoring Committee

An Independent Data Monitoring Committee (IDMC) has overall responsibility for safeguarding the interests of subjects by reviewing unblinded safety and efficacy data obtained in the study and making appropriate recommendations based on the reported data, thus ensuring that the study is being conducted with the highest scientific and ethical standards. The IDMC is also responsible for reviewing the data generated and for recommending on subsequent actions to be taken. These actions may include:

- Recommending modifications to the study protocol to enhance subject's safety.
- Recommending the termination of the study at any time if major concerns arise regarding the safety of ponesimod.

The IDMC is composed of physicians with relevant medical expertise (including a neurologist, a neurovirologist, a neurologist with MRI expertise or a neuroradiologist, a cardiologist, a pulmonologist), and a statistician and will be fully operational prior to enrolment of the first subject into the study. The composition and operation of the IDMC are described in the IDMC charter.

3.4.2 Statistical Analysis Center

A Statistical Analysis Center (SAC), a Contract Research Organization (CRO) not otherwise involved in study conduct or statistical analysis, will generate all unblinded analysis reports, throughout the trial period, exclusively for review by the IDMC. The unblinded reports will be generated from blinded efficacy and safety data periodically transferred to the SAC.

3.4.3 Ophthalmology Safety Board

An Ophthalmology Safety Board (OSB) composed of two independent ophthalmologists will review and evaluate in a blinded fashion any new or suspected cases of macular edema. The composition and operation of the OSB are described in the OSB charter.

3.4.4 Major adverse cardiovascular events adjudication board

A major adverse cardiovascular events (MACE) adjudication board will review and evaluate in a blinded fashion the MACE reported in the study. The selection of AEs that will be sent for adjudication will be based on a pre-defined list of preferred terms belonging to relevant Standardized MedDRA Queries. For each AE sent for MACE adjudication, the

MACE adjudication board will determine whether the event belongs or not to one of the pre-specified categories including cardiovascular death, myocardial infarction, and stroke.

The composition and operations of MACE adjudication board will be described in the MACE adjudication board charter.

4 SUBJECT POPULATION

4.1 Subject population description

This study will enroll adult male and female subjects aged 18 to 55 years with established diagnosis of MS, as defined by the 2010 revision of McDonald Diagnostic Criteria [Polman 2011], with relapsing course from onset (i.e., RRMS and SPMS with superimposed relapses). The trial will include up to 15% of subjects with SPMS with superimposed relapses, but no forced randomization is planned.

Subjects must have active disease evidenced by one or more MS attacks within the period of 12 to 1 months prior to baseline EDSS assessment, or by two or more MS attacks within the 24 to 1 months prior to baseline EDSS assessment, or with one or more Gd+ lesion(s) of the brain on an MRI performed within 6 months prior to baseline EDSS assessment. The MRI assessed at Visit 2 (Baseline) may be serving as the qualifying scan. Enrolled subjects must be ambulatory with an EDSS score of up to 5.5 inclusive. The subjects may be treatment-naïve (i.e., no MS disease-modifying therapy received at any time in the past) or previously treated with IFN β -1a, IFN β -1b, glatiramer acetate, dimethyl fumarate, or natalizumab.

Subjects with significant medical conditions or therapies for such conditions (e.g., cardiovascular, pulmonary, immunological, hepatic, ophthalmological) are not eligible to enter the study.

Eligible subjects must be able and willing to give informed consent for participation in the clinical study.

4.2 Rationale for the selection of the study population

RMS is the most frequent presentation of MS. Despite multiple therapies available, many subjects continue to experience relapses and accumulate disability.

Subjects with SPMS represent a significant unmet medical need for new therapeutic options. These subjects have generally been less studied and have often not been included in pivotal trials of medications approved for treatment of RMS. For these reasons, it is important to also evaluate the benefit/risk profile of ponesimod in subjects with SPMS with superimposed relapses.

The clinical relevance of McDonald 2010 Diagnostic Criteria, including subjects with only one attack, in the presence of supplementary clinical and/or MRI criteria as well as the value of early treatment in MS are widely recognized.

The study will enroll subjects with recent evidence of active disease as determined by clinical or imaging criteria, as these are prognostic factors that identify a patient population in whom effective disease-modifying treatment is particularly indicated.

The study will recruit adult subjects, restricted to subjects between 18 and 55 years of age, as non-MS-specific MRI lesions can appear more frequently in older age. Such lesions and other CNS changes due to aging make the assessment of MS more difficult and may affect the response to treatment, which could result in inconclusive trial results. The age range of the study population will be representative of the general RMS population.

Subjects with an EDSS score 0–5.5 may have developed mild to moderate impairment but are still ambulatory. The clinical care and management of these subjects is compatible with their inclusion in clinical trials. Outcomes measured in this study require ambulatory subjects (e.g., MSFC). The subjects with EDSS above 5.5 will often have SPMS with declining disease activity and would therefore make the study population too heterogeneous for testing a disease-modifying potential of a new MS compound.

Subjects with significant cardiovascular, pulmonary, immunological, hepatic, or ophthalmological medical conditions or therapies are excluded since such conditions/therapies have the potential to put the subject at increased risk of adverse drug reactions, and/or interfere with the treatment effect, study assessment and interpretation of study results.

4.3 Inclusion criteria

For inclusion in the study, all of the following inclusion criteria must be fulfilled. It is not permitted to waive any of the criteria for any subject:

- 1. Signed informed consent prior to initiation of any study-mandated procedure.
- 2. Males and females aged 18 to 55 years (inclusive).
- 3. Subjects of reproductive potential are eligible only if the following applies:
 - WOCBP:
 - must have a negative serum pregnancy test at Visit 1 (Screening) and a negative urine pregnancy test at Visit 2 (Baseline);
 - must agree to undertake 4-weekly urine pregnancy tests during the study and up to 6 weeks after the first of two tests showing teriflunomide plasma level < 0.02 mg/L;

5 December 2018, page 80/376

- must agree to use reliable methods of contraception from Visit 1 (Screening; see Section 4.5.1) until 6 weeks after the first of two tests showing teriflunomide level < 0.02 mg/L.
- Fertile male subjects participating in the study who are sexually active with WOCBP:
 - must agree to use a condom during the treatment period and for an additional
 6 weeks after the first of two tests showing teriflunomide level < 0.02 mg/L.
- Definition of WOCBP, fertile male subjects and the reliable methods of contraception for this study are described in Section 4.5.
- 4. Presenting with a diagnosis of MS as defined by the revised (2010) McDonald Diagnostic Criteria for MS [see Appendix 1], with relapsing course from onset (i.e., RRMS, or SPMS with superimposed relapses).
- 5. Having experienced one or more documented MS attacks with onset within the period of 12 to 1 months prior to baseline EDSS assessment, or two or more documented MS attacks with onset within the period of 24 to 1 months prior to baseline EDSS assessment, or having one or more Gd+ lesion(s) of the brain on an MRI performed within 6 months prior to baseline EDSS assessment (MRI assessed at Visit 2 [Baseline] may be the qualifying scan).
- 6. Treatment-naïve or previously treated with IFN β -1a, IFN β -1b, glatiramer acetate, natalizumab, or dimethyl fumarate.
- 7. Ambulatory and with an EDSS score between 0 and 5.5 (inclusive) at Visit 1 (Screening) and Visit 2 (Baseline).
- 8. Agreeing to use an accelerated elimination procedure for teriflunomide after the last dose of study drug [see Section 5.1.14 for the description of the accelerated elimination procedure].

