Periods		PRE-RANDC	MIZATION									
	Name	(1	(1)		TREATMENT PERIOD							
	Duration	Up to 4	5 Days	108 Weeks								
Visits	Number	1	2	3	4	5	6	7	8-9	10		
	Name	Screening	Baseline	Rand	W2	W4	W12	W24	W36 - 48	W60		
	Time	Day -4	5 to -1	Day 1	Day 15	Week 4	Week 12	Week 24	Week 36 – 48	Week 60		
	Visit window			-	$\pm 1 \text{ day}$	$\pm 3 \text{ days}$	\pm 7 days	\pm 7 days	\pm 7 days	\pm 7 days		
Informed conso	ent*	Х				2			, i i i i i i i i i i i i i i i i i i i	· · · ·		
Inclusion/exclu	usion criteria*	Х	Х	Х								
Demographics	*	Х										
Medical histor	y / smoking status*	Х	Х									
MS history & t	treatment*	Х										
McDonald crit	eria (revision 2010)	Х										
EDSS/FS*	· · ·	Х	Х				Х	Х	Х	Х		
Relapse* (2)	Relapse* (2)		Х	X (2) <						> X (2)		
MSFC*, SDM	Т *	X(3)	X(3)	X(3)			Х	Х		Х		
FSIQ-RMS**	(4), PGI-S**, CGI-C*		X(5)				Х	Х		Х		
SF-36v2**			Х				Х	Х		Х		
Health care resource utilization* (6)					Х	Х	Х	Х	Х	Х		
WPAI:MS**			Х				Х	Х		Х		
Patient prefere	nce questionnaire** (7)	Х	Х									
Chest X-ray* ((8)	Х										
eC-SSRS**			Х							Х		
MRI** (9)			Х							Х		
Concomitant m	nedications*	Х	Х	Х	Х	Х	Х	Х	Х	Х		
Physical exami	ination*	Х	Х			Х	Х	Х		Х		
Dermatologica	l examination* (10)		Х							Х		
Body weight a	nd height* (11)	Х								Х		
Body temperat	ure*	Х	Х	Х	Х	Х	Х	Х	Х	Х		
SBP/DBP*		Х	Х	X(12)	Х	Х	Х	Х	Х	Х		
12-lead ECG**	* (13)	х	Х	X(14)	Х	х	X(15)	Х	Х	Х		
Ophthalmologi	ical examination* / OCT* (16)	Х					Х	Х		Х		
PFT** (17)			Х			Х	Х			Х		
Hematology/C	hemistry** (fasted)	Х	Х		Х	X (1	8) <>	· X (18)	Х	Х		
Urinalysis		Х				Х	Х	Х		Х		
Tuberculosis te	est / Viral serology **	Х										
Additional seru	um sample for viral serology		Х									
Pregnancy test	*/**	X (19)	Х		Х	Х	Х	Х	Х	Х		
PK sampling for	or ponesimod* (20)			х			Х			Х		
Study drug dis	pensing & accountability											
(21)*/**				Х	Х	Х	Х	Х	Х	Х		

Ponesimod / ACT-128800 Relapsing multiple sclerosis Protocol AC-058B301, OPTIMUM Version 7 5 December 2018, page 46/376

Confidential

Study drug swallowing test (optional)		Х							
AEs*/SAEs(22)	Х	Х	Х	Х	Х	Х	Х	Х	Х

*Data collected in the eCRF

**Data electronically transferred to sponsor.

Day 1 (date of randomization visit) is to be used as the reference date for the purpose of calculating the subsequent visit dates (and time windows).

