(1) All pre-randomization assessments performed at Visit 1 (Screening) and Visit 2 (Baseline) may be conducted on days differing from the actual Visit 1 (Screening) date defined as the start of screening activities (i.e., signature of the informed consent form) and Visit 2 (Baseline)date defined as the date of baseline EDSS assessment. However, all pre-randomization assessments performed at Visit 1 and repeated at Visit 2 (Baseline; e.g., hematology, blood chemistry, urinalysis, physical examination, central laboratory, 12-lead ECGs, and SBP/DBP) must be performed at least 7 days after the Visit 1 (Screening) assessments. For women of childbearing potential, the serum pregnancy test at Visit 1 (Screening) must be performed at least 3 weeks before the urine pregnancy test performed pre-randomization at Visit 2. The blood draw at Visit 2 (Baseline) should happen early enough in order obtain the results from the central laboratory and confirm the eligibility prior to randomization.

- (2) At every study visit, subjects are reminded to contact their principal investigator / treating neurologist at the clinical site immediately in the event of the appearance of any new or worsening neurological symptoms. In addition, the site will contact the subject in between the 12-weekly visits (e.g., Visit 6–Week 12, Visit 7–Week 24,...) in order to proactively inquire about any new or worsened neurological symptoms. These telephone calls will be conducted either at Weeks 18, 30, 42, 54, 66, 78, 90, and 102 (+/- 7 days), or 6 weeks after the last 12-weekly visit (+/- 7 days). Whenever, between visits, a subject experiences any new or worsening neurological symptoms, he/she must contact the principal investigator / treating neurologist, study nurse or clinical coordinator as soon as possible in order to complete a relapse assessment questionnaire [see Appendix 17].
- (3) During pre-randomization, two practice tests and a third test serving as baseline assessment will be performed. Ideally, the three tests should be performed ≥ 5 days apart (i.e., second test practice ≥ 5 days from first practice test and third test serving as baseline ≥ 5 days from second practice test). The first test practice may be done at Visit 1 (Screening), the second test practice may be done at Visit 2 (Baseline) and the third test serving as baseline may be performed pre-dose at Visit 3 (Randomization).

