- (17) Pulmonary function tests include spirometry to be performed pre-dose in all subjects and DL_{CO} to be performed in a subset of approximately 400 subjects at selected sites only.
- (18) In addition, liver tests (ALT, AST, INR, alkaline phosphatase and total bilirubin) at Weeks 6, 8, 10, 14, 16, 18, 20, and, 22 will be collected, sent to, and analyzed at the central laboratory. Furthermore, total white blood cell and total lymphocyte counts will be assessed at Weeks 8, 16, and 20. The test window is ± 3 days. Note: No relapse assessment questionnaire is needed when blood sample is drawn.
- (19) Serum pregnancy test at Screening, urine pregnancy test at all subsequent visits. Urine pregnancy tests (performed at home) on a 4-weekly (+/- 4 days) basis between the visits during the study (results to be communicated by telephone call to the principal investigator / treating neurologist). At all visits and telephone calls, the methods of contraception will be reviewed and the contraceptive method form entered in the eCRF must be updated as applicable.

(20) Pharmacokinetic sampling pre-dose at Weeks 12, 60 and 108, and 3 h (+/-15 min) post-dose on Day 1 and Week 12.

(21) Scheduled study medication dispensing/return procedures may be adapted according to the site practice.

(22) All AEs and SAEs that occur after signing the Informed Consent Form and up to 30 days after study treatment discontinuation must be reported.

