- (5) In case of premature study drug discontinuation, the chest X-ray at EOT does not need to be performed if the EOT visit occurs within less than 24 weeks of the pre-randomization chest X-ray.
- (6) Brain MRI to be performed at any time an opportunistic infection in the CNS is suspected. In addition, non-conventional MRI techniques (MTR and DIR) will be performed at selected sites only. Note: in case of premature study treatment discontinuation, the MRI assessment at EOT does not need to be performed if the EOT visit occurs within less than 4 weeks of the MRI assessment at Visit 10 (Week 60).
- (7) Dermatological examination to be performed by a dermatologist.
- (8) SBP/DBP: Pre-dose and hourly (+/-15 min) for at least 4 h post-dose and up to 12 h.
- (9) Pre-dose ECGs at all visits (when applicable) except re-initiation visits. At re-initiation, pre-dose and hourly (+/- 15 min) for at least 4 h post-dose ECGs and up to 12 h.
- (10) OCT and/or ophthalmological examination to be performed at any visit in the presence of visual symptoms suggestive of macular edema or active uveitis [see Section 5.1.13.7].
- (11) PFTs include spirometry to be performed pre-dose in all subjects and DL_{CO} to be performed in a subset of approximately 400 subjects at selected sites only.
- (12) Serum pregnancy test at FU2. Urine pregnancy test at all other visits. Urine pregnancy tests (performed at home) on a 4-weekly basis between the visits during the study and continued after last study drug intake on a 4-weekly basis (+/- 4 days) (performed at home) until 6 weeks after the first of two tests showing teriflunomide plasma level < 0.02 mg/L (results of the pregnancy tests to be communicated by telephone call to the principal investigator / treating neurologist). At all visits and telephone calls, the methods of contraception will be reviewed and the contraceptive method form entered in the eCRF must be updated as applicable.

- (13) Pre- and post-vaccination sampling for vaccine-specific antibody titers for subjects having received non-live vaccination while on study treatment (sub-study)

(14) When possible, collect PK sample upon experiencing SAE. Preferably, sample will be collected pre-dose, as early as possible after SAE onset, and no later than 7 days after the last dose of study drug.

- (15) If the subject was not compliant with the accelerated elimination procedure, the procedure must be repeated or missing intakes completed.

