3.1.1 Pre-randomization period

This period starts up to 45 days before randomization at the time of the signature of the Informed Consent Form (ICF) and ends with subject's randomization. It includes Visit 1 (Screening) and Visit 2 (Baseline).

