At Visit 3 pre-dose (Day 1), the first-dose administrator must provide the ECG results and interpretation to the principal investigator / treating neurologist and support her/him, if requested, to make a final decision on the subject's eligibility according to the inclusion/exclusion criteria. At Visit 3 (Day 1), the pre-dose ECG must be performed prior to randomization and the applicable points from exclusion criterion #18 (e.g., HR < 50 bpm, presence of second-degree AV block Mobitz Type II or third-degree AV block, or a QTcF interval > 470 ms (females), > 450 ms (males), see Section 4.4) must be ruled out.

During the treatment period ECGs must be performed at pre-dose. Additionally, at Visit 6 (Week 12) during the treatment period, ECGs must also be performed at 3 h post-dose. In case of need of concomitant treatment with a QT-prolonging drug with known risk of Torsades de Pointes, additional ECGs will be performed according to the guidance provided in Appendix 3.

At Visit 3 (Day 1) and on the day of re-initiation of study drug when post-dose monitoring is required [see Section 5.1.10], ECGs must be performed at pre-dose, and hourly (+/- 15 min) thereafter for a minimum of 4 h and up to 12 h post-dose. Subjects may be discharged from the cardiac monitoring if they meet the discharge criteria before 12 h post-dose but no sooner than the (report of) ECG at 4 h post-dose has been evaluated by the first-dose administrator [see Section 5.1.11]. If the subject does not meet the defined discharge criteria at 12 h post-dose, the subject will be permanently discontinued from the study drug but will continue to be monitored, and additional ECG measurements will be performed until changes in ECG variables are no longer clinically relevant [i.e., discharge criteria are met; see Section 5.1.11], or until medically indicated.

On Day 1 and on the first day of re-initiation of study drug when post-dose monitoring is required, significant findings, which in view of the first-dose administrator meet the definition of a (non-serious) AE, have an onset after the study drug intake, and are resolved at the time of discharge of the subject from cardiac monitoring, must be recorded directly on the AE page of the eCRF by the first-dose administrator. These AEs will not be visible

Ponesimod / ACT-128800 Relapsing multiple sclerosis Protocol AC-058B301, OPTIMUM Version 7 5 December 2018, page 135/376

Confidential

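### Table 1 and inclusion criterion 3 do not clearly call for a pregnancy test on Day 1, although footnote (19) by its wording covers that visit; the last required negative test can be up to 24 days old at first dose

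*Protocol*

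**What the plan says.** Four places in the protocol bear on the timing of pregnancy tests before the first dose.

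- **Section 4.3, criterion 3.** A woman of childbearing potential "must have a negative serum pregnancy test at Visit 1 (Screening) and a negative urine pregnancy test at Visit 2 (Baseline"). She must also agree to 4-weekly urine tests during the study. No Day 1 result is named. The synopsis likewise asks only for a negative test in the pre-randomization period.
- **Table 1, pregnancy-test row.** Eight of the nine visit columns are marked. The only blank is Visit 3. The same table treats that day as a visit: "Day 1 (date of randomization visit) is to be used as the reference date".
- **Table 1, footnote (19).** "Serum pregnancy test at Screening, urine pregnancy test at all subsequent visits". It adds home urine tests every 4 weeks (+/- 4 days) "basis between the visits during the study". Its marker is on the Screening cell only.
- **Table 1, footnote (1), and Section 3.1.1.** The serum test "must be performed at least 3 weeks before the urine pregnancy test performed pre-randomization at Visit 2". On the length of the pre-randomization period, Section 3.1.1 says: "This period starts up to 45 days before randomization".

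Table 2 has a parallel footnote (12): "Serum pregnancy test at FU2. Urine pregnancy test at all other visits". There the marker is on the row label as well as on the FU2 cell, and all six scheduled visits are marked.

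**The concern.** Sites can read these instructions in two ways. One that takes footnote (19) at its word tests on Day 1. One that works from the grid and criterion 3 does not, and its last required negative result is the one from Visit 2.

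What is at stake is fetal exposure. Section 1.3.3 says that pregnancy has to be ruled out before teriflunomide is started, and Section 1.3.2.4 reports embryotoxic and teratogenic potential for ponesimod. Treatment is blinded, so the check has to hold for every randomized woman of childbearing potential. Under Section 5.1.13.4, a pregnancy on study drug means permanent discontinuation and, if the woman wishes to continue the pregnancy, a request to unblind her treatment.

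Eligibility is re-checked on Day 1 (Table 1), and for cardiac exclusion 18 the protocol says how: "the pre-dose ECG must be performed prior to randomization". For exclusion 1 (pregnant or lactating women) the grid supplies no Day 1 result to check.

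**Working it through.** The protocol states no figure for the interval between the last test and the first dose, so there is none to reproduce. What follows is date arithmetic.

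**Inputs**
- Screening period T: at most 45 days (Section 3.1.1). Shorter values are shown for range.
- Minimum spacing from the Visit 1 serum test to the Visit 2 urine test: 3 weeks = 21 days (Table 1, footnote (1)).
- Home tests: every 28 +/- 4 days, that is 24 to 32 days (footnote (19)).
- Next marked test after Visit 2: Day 15 +/- 1 day (Table 1).
- First dose: Day 1, one dose daily.

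**Age of the Visit 2 test at first dose, following the grid**

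The minimum is 1 day (test on Day -1). The maximum is T - 21:

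| T (days) | Longest gap (days) |
|---|---|
| 28 | 28 - 21 = 7 |
| 35 | 35 - 21 = 14 |
| 45 | 45 - 21 = 24 |

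**Doses taken before the next marked test**

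Not counting the visit-day dose, a visit on Day 14 follows 13 doses and a visit on Day 16 follows 15 doses. The range is 13 to 15.

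**Would a home test fall inside the gap?**

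Footnote (19) does not say from which date the 4 weeks run, so both starting points below are assumptions.

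- *From Visit 1:* age at first dose runs from T - 32 to T - 24. For T = 45 this is 13 to 21 days. For T = 35 it is 3 to 11 days. For T = 28 it is -4 to 4 days, so the test may fall after the first dose.
- *From Visit 2:* the home test comes 24 to 32 days after the Visit 2 test. That test is at most 24 days old at first dose, so the home test falls on the dosing day at the earliest and usually later.

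A home test may therefore shorten the gap, but whether it does depends on a starting date that footnote (19) does not state.

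**With a Day 1 test before randomization** the gap is 0 days.

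**The case against.** There is a fair case on the other side.

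- **Footnote (19) may state only the type of test.** Its marker is on the one serum visit in Table 1, so it can be read as serum there and urine at the other marked visits. Table 2 gives this some support: footnote (12) speaks of all other visits, yet the relapse and re-initiation columns of that row are blank. This stands. A reader might infer that footnote (19) mandates a Day 1 test which the grid and criterion 3 then drop. The documents do not establish that, because criterion 3, footnote (1) and the grid agree with one another and the synopsis is compatible with them. Against the type-only reading, the blank columns in Table 2 are unscheduled visits. At scheduled visits in Tables 2 and 3 the wording and the grid agree, and Day 1 is the one scheduled visit where they differ.
- **Section 8.2.1.1 may settle it.** It covers the Visit 3 pre-dose assessments and is listed in the contents, but its text was not available here. If it lists the test, most of the safety concern goes and the mismatch in Table 1 remains.
- **Contraception is required from Visit 1.** A hormonal method from Group 1 must have been taken for at least 30 days before randomization, longer than the 24-day maximum gap. This lowers the risk considerably. However, a non-hormonal method need only be in place by Visit 2 (Section 4.5.1), so the Visit 2 test could miss a very recent conception.
- **Home tests may start at consent.** Section 5.2.1 equates the start of the study with signing consent. Even then the last test is 13 to 21 days old when T = 45. It is also true that 24 days does not exceed the protocol's own 24-to-32-day home-testing interval, but that interval is for monitoring during the study, not for ruling out pregnancy before a first dose.
- **Other exclusions rest on Visits 1 and 2.** The hematology and liver-enzyme criteria do, and exclusion 18 itself names Day 1, so the comparison with the ECG carries limited weight.

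**Conclusion.** The point holds as an ambiguity with a small safety cost. Footnote (19) by its wording reaches Day 1, while the grid and criterion 3 stop at Visit 2. A site following the latter two could dose up to 24 days after the last required negative test, and 13 to 15 doses could be taken before the next test in the grid. The 24 days is a worst case: it assumes the full 45-day screening period, the minimum 21-day spacing, no home test in between, and no Day 1 test in Section 8.2.1.1. With 28-day screening the maximum is 7 days.

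It would be wrong to conclude that women will usually be dosed on a 24-day-old result, or that nothing else protects them. Two negative tests at least 3 weeks apart and mandatory contraception are in place; they reduce the risk without reliably removing it.

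A Day 1 test is worth having under either reading of footnote (19). It is a cheap improvement for patient safety, with no bearing on alpha, power, sample size or the efficacy analysis.

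**What to change.** - In Table 1, mark a urine pregnancy test before randomization at Visit 3 (Day 1), and put marker (19) on the row label, as Table 2 does with (12).
- In Section 4.3, criterion 3, add a negative urine pregnancy test on Day 1 before randomization.
- Align Section 8.2.1.1 if it does not already say this.

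The cost is one urine test per woman of childbearing potential at a visit already held, a short wait for the result before randomization, and a few words in the table and the criterion.
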